Specific Aim 1: To test the hypothesis that irritant-induced asthma is characterized by elevated markers of inflammation in a manner similar to that described for allergic asthma.

SA1.a We will identify and phenotype individuals with WTC dust cloud-exposed irritant-induced asthma (IA), individuals with allergic asthma (AA) and healthy unexposed individuals (Controls).

SA1.b We will measure biomarkers of inflammation using noninvasive techniques for exhaled nitric oxide (ENO) and 8-isoprostanate from exhaled breath condensate (EBC) in WTC irritant-induced asthma (IA), individuals with allergic asthma (AA) and in healthy unexposed individuals (Controls).

SA1.c We will measure inflammatory cells in induced sputum from individuals with IA, AA and Controls.

Specific Aim 2: To test the hypothesis that the miRNA expression in airway epithelial cells will differ between IA, AA and Control individuals.

SA2.a. We will isolate RNA from epithelial cells and inflammatory cells in induced sputum and assess the miRNA expression profile using microarray technology among individuals with irritant-induced asthma (IA), individuals with allergic asthma (AA) and healthy unexposed individuals (Controls).

SA2.b. We will identify the mRNA targets of the differentially expressed miRNAs by using publicly available databases and correlate miRNA and mRNA expression.

Specific Aim 3: To test the hypothesis that levels of RNA of targets in human sputum cells will differ before and after the administration of inhaled corticosteroids in asthmatics (both IA, AA). The importance of this hypothesis in the characterization of irritant induced and allergic asthma is to further characterize the regulatory pathways expressed in sputum cells by identifying which inflammatory markers are steroid sensitive and steroid resistant.

SA3.a. We will isolate RNA targets in discrete sputum cells from induced sputum in IA and AA individuals and compare levels before and after administration of inhaled corticosteroids.

I. Background and Significance

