Most miRNA bind to target-3'UTR and function as translational repressors most often by promoting the degradation of mRNA. Each miRNA may regulate up to 200 target genes (42). We therefore propose to correlate patterns of miRNA changes in our defined populations, with mRNA expression arrays. HMW RNA from isolated epithelial cells will be used for hybridization to Affymetrix HG-U133 Plus 2.0 microarrays. Images will be analyzed in the core facility and data will be normalized as follows: (1) per array, by dividing the raw data by the 50th percentile of all measurements; and (2) per gene, by dividing the raw data by the median expression level for all the genes across all arrays in a data set. We will determine whether up or down-regulated mRNAs are potential targets for previously identified miRNAs.

Specific Aim 3: To test the hypothesis that levels of RNA of targets in human sputum cells will differ before and after the administration of inhaled corticosteroids in asthmatics (both IA, AA). The rationale for this aim of the study is to

investigate which markers are steroid sensitive and which are steroid resistant which would provide information for therapeutic targeting in asthma.

SA3.a. We will isolate RNA targets in discrete sputum cells from induced sputum in IA and AA individuals and compare levels before and after administration of inhaled corticosteroids.

In this second phase of the study, (Phase II) we will enroll AA or IA individuals who have fit enrollment criteria for the phase I part of the study and participated in phase I of the study and were able to provide us with an acceptable sputum sample. These participants will be recontacted for participation in Phase II if they signed permission to be re-contacted. We will obtain a repeat sputum sample as baseline for the Phase II study. An inhaled corticosteroid (Fluticasone HFA 220 mcg, 1 puff twice daily) and large volume spacer will be provided. Inhalation technique and a daily diary will be reviewed. Subjects will be instructed to use Fluticasone propionate 220 mcg q puff twice daily and to record their use in a written diary. A repeat sputum sample will be obtained after 2 weeks of Fluticasone propionate use.

Sputum samples will be processed for discrete cells and RNA levels (mRNA, miRNA) will be analyzed to understand the effect of ICS use on RNA expression in discrete sputum cell populations.

Statistical Analysis:

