We will obtain epithelial cells from the lining of the nose using a technique called nasal brushing. This is a simple, nonsurgical procedure and is well tolerated by most people. We will gently brush the inside of the lateral wall of each nostril with a small, delicate, sterile brush. This procedure takes about 5 seconds for each nostril.

We also propose to correlate patterns of miRNA changes in our defined populations, with mRNA expression arrays. HMW RNA from isolated epithelial cells will be used for hybridization to Affymetrix HG-U133 Plus 2.0 microarrays. Images will be analyzed in the core facility and data will be normalized as follows: (1) per array, by dividing the raw data by the 50th percentile of all measurements; and (2) per gene, by dividing the raw data by the median expression level for all the genes across all arrays in a data set. We will determine whether up or down-regulated mRNAs are potential targets for previously identified miRNAs.

Phase II

Only subjects with Irritant asthma or Allergic asthma who have successfully completed the first phase of the study and have signed consent to be re-contacted will be recruited for the second phase of the study (Phase II). Phase II will involve two visits over a 2 week time period. For Phase II, we will first obtain sputum samples for a baseline analysis of cells. Study subjects will be provided with an inhaled corticosteroid, Fluticasone propionate HFA 220 mcg, 2 puffs twice a day (Treatment), or no treatment (No treatment). Fluticasone HFA will be provided by the study physician through the CTSI and the Bellevue Pharmacy. Treatment cases will be instructed to self administer the medication with a large volume spacer that will be provided to them. Inhaler teaching will be performed by study physician or coordinator at the time that the subject is provided the inhaler. Treatment Cases and No treatment controls will be provided a diary to record fluticasone inhaler. Treatment cases and No treatment controls will be allowed to use their usual rescue bronchodilator (albuterol) on an as needed basis. Treatment Cases and No treatment controls will return after 2 weeks for a repeat sputum induction.

2. Data Analysis and Data Monitoring:

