Induced sputum: Sputum induction involves inhalation of hypertonic saline aerosol, a stimulus known to cause bronchoconstriction in asthmatic subjects. To ensure participant safety during sputum induction we will follow the following protocol: procedure will be performed in a hospital setting by highly trained and experienced staff, administration of a bronchodilator can be given to inhibit hypertonic saline-induced bronchoconstriction, we will limit the sputum induction to 20 minutes and monitor the participant's symptoms closely with repeat spirometry every 2 minutes after induction. If bronchoconstriction occurs we will follow the protocol discussed under MCT.

Nasal brushing: Nasal brushing. We do not anticipate any untoward risk of performing this procedure in normal individuals or in those with asthma. This procedure is not usually painful but some people experience a moment of discomfort for about 5 seconds during the brushing. There may be minor irritation such as reflex tearing from your eyes, or sneezing. There may be a rare chance that there is a small amount of bleeding as if you had a scrape. These possible discomforts resolve on their own.

Administration of inhaled corticosteroid –We are providing high dose inhaled corticosteroid (*Fluticasone propionate HFA 220 mcg*) for a short (2 week) period of time. This medication poses no more than minimal risk to research subjects and the risk is minimized by the short treatment period and the use of a large volume spacer. This is an approved treatment for asthma. The most common symptoms experienced by patients who have taken fluticasone are: upper respiratory infections (25-29%), hoarseness or dysphonia (1-4%), inflammation of throat, nose or sinuses (1-12%), oral candidiasis (2%) , nausea and vomiting (1%), other gastrointestinal symptoms (1-2%), and muscle or bone pain (3%). Subjects will be instructed to avoid oral candidiasis by rinsing their mouth after administration of the medication.

2. Protection against Risks:

All participants will be provided with a contact physician capable of providing sources of appropriate medical or professional intervention in the event of adverse effects to the subject. This person will be available on a 24 hour contact basis through the New York University/Bellevue Hospital Asthma Clinic hot line.

3: Potential Benefit to the Subjects:

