The consent form will be written and oral. When it is needed the services of a translator will be provided. Attached is a copy of the informed consent that will be presented to subjects. A second consent form will be provided to asthmatic patients who have completed Phase I of the study and wish to continue on to Phase II of the study with administration of inhaled corticosteroid. Attached is the copy of the consent form for phase II of the study that will be presented to subjects. The consent process will take place in the CTSI rooms. Confidentiality and privacy of the patients will be maintained. The patient will have the opportunity to ask questions to the physician. The Clinical Coordinator and the physician will obtain consent from the subjects. Time will be allotted for a period of Question and Answer in which the patient will have the opportunity to have all their concerns addressed by the physician regarding the study. Primary recruitment will be with patients who understand English. The questionnaires are only available in English, and if required translations services will be requested.

3. Subject Capacity: 90 subjects (accrued and able to be included in the data analysis)

4. Subject /Representative Comprehension: Time will be allotted for a period of Question and Answer in which the patient will have the opportunity to have all their concerns addressed by the physician regarding the study.

5. Debriefing Procedures: no information will be withheld from the subject since no psychological studies will be performed.

6. Consent Forms:

All participants will have consent obtained according to the NYU-IRB consent form. Consent will be sought by a clinical coordinator and signed consent forms will be maintained for all subjects. Complete information on the procedure and potential risks of the procedure will be provided to the patient. The participant will be informed that the procedure will be of no immediate benefit to him/her but may help advance our knowledge of mechanisms of airway inflammation

7. Documentation of Consent: All consents will be signed.

8. Costs to the Subject: There will be no cost to the subject.
9. Payment for Participation: The subject will receive \$50.00 per visit.

References

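### The Phase II fluticasone regimen is one puff twice daily in one section and two puffs twice daily in another, a two-fold difference in scheduled dose that the protocol leaves unresolved

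*Combined protocol and SAP*

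**What the plan says.** The regimen, or part of it, appears in four places in the combined protocol and SAP.

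- Research Design and Methods, Specific Aim 3, SA3.a (supply): "An inhaled corticosteroid (Fluticasone HFA 220 mcg, 1 puff twice daily) and large volume spacer will be provided".
- Same paragraph (instruction to subjects): "Subjects will be instructed to use Fluticasone propionate 220 mcg q puff twice daily and to record their use in a written diary". As it reads, this gives no puff count.
- Section III.1, Phase II: "Fluticasone propionate HFA 220 mcg, 2 puffs twice a day (Treatment), or no treatment (No treatment". The section then adds: "Treatment Cases and No treatment controls will be provided a diary to record fluticasone inhaler".
- Section IV.1, Risk: "We are providing high dose inhaled corticosteroid". The strength (220 mcg) and the two-week duration follow, but no puff count or daily total.

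Section III.2 names the Phase II primary outcome, the change in TSLP expression on inhaled corticosteroid against no treatment, compared between two randomised groups planned at 15 each. It states no dose. The consent section adds: "A second consent form will be provided to asthmatic patients who have completed Phase I of the study". That form is not part of the public text.

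On a lesser point, SA3.a says the investigators will "compare levels before and after administration of inhaled corticosteroids", and its Phase II paragraph ends with "A repeat sputum sample will be obtained after 2 weeks of Fluticasone propionate use". Neither mentions the untreated group that sections III.1 and III.2 describe.

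**The concern.** The two clear dose statements describe the same Phase II treatment and cannot both be followed. The dose defines the treated arm. If it is not fixed, the primary comparison estimates the effect of an unspecified regimen, and an arm planned at 15 could contain participants on either schedule. Aim 3 also sets out to sort markers into steroid-sensitive and steroid-resistant, and that classification is hard to interpret unless the scheduled steroid dose is known.

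Two consequences follow. The diary has no settled number of scheduled puffs to be read against. The minimal-risk statement in section IV.1 is not tied to a stated daily amount.

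The Aim 3 wording matters less. It describes only a before-and-after comparison in treated participants, whereas the stated primary analysis is between groups. The aim is incomplete beside sections III.1 and III.2, not incompatible with them.

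**Working it through.** **Inputs.** Strength per puff is 220 mcg in both SA3.a and section III.1. Frequency is twice daily in both. Duration is two weeks, or 14 days, in both. Puffs per administration are 1 in SA3.a and 2 in section III.1. The plan states no daily or cumulative total, so there is no figure of its own to reproduce.

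**Formulas.** Daily dose = strength × puffs × 2. Puffs over the period = puffs × 2 × 14. Cumulative dose = daily dose × 14.

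| | SA3.a | Section III.1 |
|---|---|---|
| Daily dose | 220 × 1 × 2 = 440 mcg | 220 × 2 × 2 = 880 mcg |
| Puffs in 14 days | 1 × 2 × 14 = 28 | 2 × 2 × 14 = 56 |
| Cumulative dose | 440 × 14 = 6,160 mcg | 880 × 14 = 12,320 mcg |

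Ratio: 880 / 440 = 2.0.

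**Diary illustration.** If the diary counts puffs (an assumption, since its format is not described), 28 recorded puffs are 28/28 = 100% of schedule under SA3.a and 28/56 = 50% under section III.1.

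**Does any other text settle it?**

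- The instruction to subjects in SA3.a gives no usable count.
- The high-dose label in section IV.1 does not decide the matter, because the document does not define the term by puffs or daily total.
- Section III.2 ties no dose to its outcome or its effect size.
- Neither dose statement is limited to a subgroup, and neither belongs to an amendment log.

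**A separate inconsistency, not counted in the weight of this point.** Sputum induction runs at 2-minute intervals for up to 20 minutes in SA1.c, and at 4-minute intervals for up to 12 minutes in section III.1. Section IV.1 sets a 20-minute limit, which both schedules meet, with spirometry every 2 minutes.

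**The case against.** The conflict in puff count is not in dispute. The case on the other side is that it is narrow.

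- **Most of the regimen is fixed.** Drug, strength, frequency, spacer, duration and comparator are all stated, and only puffs per administration differ. That is correct, but the puff count alone doubles the dose.
- **Two-fold refers to scheduled study drug, not total steroid exposure.** The inclusion criteria (section II.5) allow inhaled corticosteroid use, so a participant's total exposure need not double. This stands, and the size is stated here as scheduled study drug only.
- **The unclear instruction in SA3.a may be a typing slip or a fault in reading the PDF.** This also stands. It should be checked against the source file, and the finding does not rest on it.
- **The diary point is hypothetical.** The plan defines no adherence threshold or per-protocol set, and section III.2 makes no use of the diary. The percentages are therefore an illustration, not an effect on a planned analysis.
- **Unseen text might settle the dose.** The Phase II consent form and a short stretch of the protocol before the consent section are not in the text examined. The conclusion is limited accordingly. Even so, a single dose stated elsewhere would leave SA3.a and section III.1 contradicting each other.
- **The risk section contradicts neither statement, and the Aim 3 wording is compatible with the design.** Both are fair. The changes suggested there are for consistency.

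**Conclusion.** The concern holds. The protocol gives two regimens for its only Phase II study drug, differing by a factor of exactly 2 (440 against 880 mcg per day; 6,160 against 12,320 mcg over 14 days), and the available text does not reconcile them. The arithmetic assumes that 220 mcg is the strength per puff and that two weeks means 14 days.

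This must be corrected, because it leaves open the scheduled dose in the treated arm of the primary comparison and the dose participants are to take. No stated sample size, power, significance level or test changes, and no numerical effect is claimed for the Aim 3 wording or the induction schedules. No view is taken on which regimen is right.

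**What to change.** 1. The investigators decide the regimen and state it identically in SA3.a (both the supply sentence and the instruction to subjects) and in section III.1, Phase II.
2. State the same regimen in the corticosteroid paragraph of section IV.1, so that the risk statement refers to a defined dose.
3. Check the separate Phase II consent form against it.
4. Lesser: add the untreated group to Aim 3 and SA3.a, in both the Specific Aims and the Research Design section, and to the Phase II paragraph. Do not narrow the aim to TSLP. Make clear that a within-group change in treated participants does not replace the between-group primary test.
5. Separate: the investigators reconcile the induction schedules in SA1.c and section III.1 with each other and with the limit and spirometry interval in section IV.1.

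The cost is a wording amendment to those sections plus the consent-form check, with no extra patients, visits or analyses. The document does not say whether anyone has already been treated in Phase II. If so, the regimen actually dispensed to each participant should also be established from the records and reported.

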AA: These patients will be recruited from the NYUBAR (N = 30) and advertising and will have asthma as defined by NIH guidelines (51), persistent symptoms, and absence of WTC dust exposure.

Control: These patients will be recruited from the NYUBAR (N = 30) and advertising and will have no respiratory sx, no asthma diagnosis, no WTC dust exposure. Additional appropriate inclusion and exclusion criteria will be developed for each group including tobacco use, other lung disease, timing of inhaled corticosteroids etc.

The study will entail two to three visits. On visit 1 (V1) all individuals will sign informed consent to participate in the study under an NYU IRB approved protocol. A questionnaire will be completed with standardized questions that include information on WTC exposures, demographics, presence and severity of respiratory symptoms, tobacco history and past medical history. Individuals will undergo spirometry with inhaled bronchodilator. Individuals will undergo methacholine challenge test (visit 1a) if they have normal spirometry or no bronchial hyperresponsiveness. On visit 2, individuals will return to undergo ENO, EBC and spirometry with pre and post bronchodilator maneuvers and induced sputum. Blood will be obtained for CBC with differential cell count, and assessment of total IgE and allergen-specific IgE. Blood will also be stored for future analysis of inflammatory markers. Based on our experience, we have had individuals unable to produce enough sputum and thus yield too small a number of cells. These individuals are excluded from data analysis. In addition, we also have subjects who are able to produce sputum and return for repeat sputum testing.

SA1.b We will measure biomarkers of inflammation using noninvasive techniques for exhaled nitric oxide (ENO) and 8-isoprostanate from exhaled breath condensate (EBC) in WTC IA, AA and controls.

We will use the handheld NIOX MINO® to measure ENO (Aerocrine, Sweden) (17, 18, 20, 52). The NIOX MINO® fulfills the ATS recommendations and provides reliable readings and is portable and we have experience with it (53). Most healthy individuals have ENO levels in the range of 5-35 ppb (some variation with age, gender, race/ethnicity) (54). Individuals with asthma have ENO levels that can range from 25-80 ppb and even higher (18, 61, 62).

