We were able to develop basic techniques and measurement from 10 patients in each group as initially proposed in the previous version of this protocol. We now propose to increase our enrollment from 30 to 50 subjects in each group based on the recruitment and enrollment data of about 30% of screen failures (33 subjects screen failed out of 108 total). In addition, there have been subjects who have not been able to produce sputum or provide adequate number of sputum cells for analysis (38 subjects out of 65 accrued gave adequate sputum samples). This represents about 60% success rate for sample quality. Therefore, we will need to increase our enrollment numbers to achieve an n=30 per group.

Power Analysis: Based on a similar rate of screen failures and inadequate samples, the analysis is now based on 50 patients in each group. Our group sample sizes of 50 and 50 achieve 90% power to detect a difference of 0.73 given the null hypothesis that the two-group difference is 0 and the estimated group standard deviations are 1.0 and 1.0, with a significance level (alpha) of 0.05 using a two-sided two sample t-test. We will work with [name], our biostatistician for our statistical analysis.

For ENO and EBC analyses, we will express data as means \pm SD for normally distributed variables. For variables that are not normally distributed we will use medians and the interquartile range. We will use statistical analysis including unpaired *t* tests, Kruskal-Wallis test, and regression coefficients as appropriate. P values of < 0.05 will be considered significant. Differential expression of miRNA and hierarchical clustering will be performed with the genomics core. Statistics using *t* tests or algorithms designed specifically for data mining and biochip interpretation will be used. Pathway analyses will also be performed by the genomics computational core.

Anticipated results and alternative approaches

We will continue to recruit patients with WTC exposure or with asthma based on our experience in our asthma registry or our WTC clinic, in which most people are willing and anxious to participate in any study that might help characterize their symptoms.

We plan to also submit an advertisement to the IRB for approval and to use research match (researchmatch.org) a national registry which is a secure, web-based approach as a recruitment method, and will post the advertisement.

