We have chosen to use individuals with WTC dust cloud exposure as our model of initial high dose exposure to enhance our ability to identify patients with irritant asthma. We suspect that other more prolonged exposures also induce irritant asthma, but our previous studies and those of other investigators suggest that this exposure provides the highest risk.

We have proposed a positive selection strategy for isolation of bronchial epithelial cells from IS. The possibility exists that this technique may provide too low a yield of cells. Should that be the case, we can use a negative selection strategy using anti-CD14 and anti-CD16 antibody beads to specifically deplete macrophages and neutrophils respectively (37). We may also need to obtain duplicate sputum samples from patients, i.e. have patients return for a second sputum induction.

Our initial analyses will be between our healthy controls and asthma in general (AI and AA) and subsequently between each type of asthma (AI and AA) to optimize our ability to detect differences in sputum markers and miRNA. The

possibility exists that we will find no difference between measurements of markers of inflammation in exhaled breath between AI and AA. Should that be the case, we will have to examine whether our pilot study was powered to identify a small difference.

We are basing our miRNA and mRNA studies on those that have been performed in epithelial cells derived from cigarette smokers (45). These studies have shown a correlation between mRNA and miRNA expression and thus there is precedent for our studies. Because of the high price of each of these chips, and the cost of core analysis time, we initially propose to use 5 subjects for each condition to obtain a global pattern scale. These studies will subsequently be extended to get a reasonable statistical power.

From our pilot studies and recent publication we will continue to investigate mechanisms of asthma and irritant-induced asthma. The studies are high risk but have potential for high yield, and will provide data for subsequent NIH applications for replication and further evaluation for a junior faculty member. In addition, they have potential to provide information that could help target specific interventions for asthma of different phenotypes as we proposed in phase II of the study. As such, they fit the mandate of the CTSI grants.

II. Characteristics of the Research Population

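### The Phase I power statement does not reproduce (95.1%, not 90%), and at the 30 analysable subjects per group a pairwise sputum comparison has 79.4% power

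*Combined protocol and SAP*

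**What the plan says.** The Statistical Analysis section of the combined protocol and SAP raises enrolment from 30 to 50 per group because of losses. It reports two loss rates: "33 subjects screen failed out of 108 total" and "38 subjects out of 65 accrued gave adequate sputum samples". It then gives the purpose: "Therefore, we will need to increase our enrollment numbers to achieve an n=30 per group".

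The Power Analysis paragraph that follows says that "the analysis is now based on 50 patients in each group" and continues: "Our group sample sizes of 50 and 50 achieve 90% power to detect a difference of 0.73". The remaining inputs are a null difference of 0, an SD of 1.0 in each group, alpha 0.05, and a two-sided two-sample t-test.

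Other sections bear on which number applies:

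- Research Design and Methods, SA1.a, says of subjects who yield too few sputum cells: "These individuals are excluded from data analysis". It adds that "we also have subjects who are able to produce sputum and return for repeat sputum testing".
- Section II, item 1 (Number of Subjects) gives 90 subjects able to produce sputum and estimates 300 consented, screen failures included. The Subject Capacity item also gives 90, as the number that can enter the data analysis.
- Anticipated results and alternative approaches plans controls vs pooled asthma first, and "subsequently between each type of asthma (AI and AA) to optimize our ability to detect differences in sputum markers and miRNA".

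**The concern.** All the inputs to the power statement are given, so it can be checked directly, and its three figures (50 per group, 0.73 SD, 90%) do not fit together. The statement also uses the group size before sputum losses, although the paragraph above it says that the 50 is there to deliver 30.

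The comparison most exposed is irritant vs allergic asthma on sputum cells (SA1.c). Aim 1 hypothesises that inflammation in the two types is similar, so a missed difference could be read as support for that hypothesis. The plan also says that, if exhaled-breath markers do not differ between the two types, it will ask whether the study was powered for a small difference. That needs a correct power figure tied to the number of subjects each endpoint actually has.

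**Working it through.** **Inputs.** From the Power Analysis paragraph: d = 0.73 (difference 0.73, SD 1.0), two-sided alpha 0.05, two-sample t-test, 50 vs 50. From the Statistical Analysis section: target 30 per group; 33 of 108 screen failures; 38 of 65 accrued with adequate sputum.

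**Formula.** With noncentrality δ = d / √(1/n₁ + 1/n₂) and df = n₁ + n₂ − 2, power is the probability that a noncentral t(df, δ) variable exceeds the two-sided critical value in absolute size.

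**The plan's own figure.** 50 vs 50: δ = 0.73 / √(2/50) = 3.65, df = 98, critical value 1.984. Power is 95.1% (95.4% by the normal approximation). The stated 90% does not reproduce.

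**Other group sizes at d = 0.73**

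| Groups | δ | df | Power |
|---|---|---|---|
| 50 vs 50 | 3.65 | 98 | 95.1% |
| 41 vs 41 | 3.31 | 80 | 90.4% |
| 40 vs 40 | 3.26 | 78 | 89.7% |
| 35 vs 35 | 3.05 | 68 | 85.3% |
| 30 vs 30 | 2.83 | 58 | 79.4% |
| 29 vs 29 | 2.78 | 56 | 78.0% |
| 60 vs 30 (pooled asthma vs controls) | 3.26 | 88 | 89.8% |

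Simulation agrees with the 50, 41, 35, 30, 29 and 60 vs 30 rows to 0.1 percentage point.

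**Detectable differences.** With 90% power: 0.655 SD at 50 vs 50, 0.85 SD at 30 vs 30, 0.733 SD at 60 vs 30. With 80% power at 30 vs 30: 0.74 SD. So 0.73 SD goes with about 41 per group at 90% power, or about 30 per group at 80%.

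**What the 50 counts.** The text does not say.

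- If it means accrued after screening: 50 × 38/65 = 29.2 evaluable, which matches the target of 30.
- If it means consented: between 50 × 38/108 = 17.6 and 50 × (75/108) × (38/65) = 20.3 evaluable, which does not match.

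The range arises because 108 − 33 = 75 did not fail screening but only 65 are reported as accrued, and the other 10 are not explained.

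**The 300 consented.** At the same rates, 300 × 38/108 = 106 to 300 × (75/108) × (38/65) = 122 would be evaluable, or 35 to 41 per group if split equally. Conversely, 90 evaluable needs 90 / [(75/108) × (38/65)] = 222 to 90 / (38/108) = 256 consented. The 300 may contain a margin; it does not contradict the target of 90.

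**The case against.** Several points on the other side have weight.

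- **The slip at 50 vs 50 is conservative.** A design with 95.1% power does achieve 90%. This is true of the arithmetic alone, but at 30 per group the sentence is optimistic for pairwise sputum comparisons.
- **Enrolment may deliver more than 30 per group.** If all 300 consent and groups are equal, 35 to 41 per group gives about 85% to 90% power at 0.73 SD. Repeat sputum induction could also raise the yield. Both stand as possibilities, but the plan's stated analysable target is 90 in total, so 30 per group is the number to plan on.
- **The first planned contrast is hardly affected.** Pooled asthma vs controls keeps 89.8%. That is correct, but the sentence describes 50 and 50, not 60 and 30.
- **Exhaled-breath and blood markers do not need sputum.** They may keep up to 50 per group and 95.1% power. The text does not say whether the exclusion for inadequate sputum covers them.
- **A stricter alpha might explain the 90%.** At 50 vs 50, alpha 0.025 gives 91.3% and 0.05/3 gives 88.5%. The sentence states 0.05, and no adjustment is described.
- **This is a pilot, and the loss is modest.** At 30 per group the design still has 80% power for 0.74 SD. The figure also assumes a t-test on one marker, so it is only indicative for Kruskal-Wallis tests or the eosinophil and neutrophil cut-offs. These points limit the consequence, but a specific numerical claim should still be right.

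**Conclusion.** The concern holds. The sentence is wrong on its own inputs: 95.1%, not 90%. At the plan's analysable 30 per group, a pairwise sputum comparison has 79.4% power at 0.73 SD (78.0% at the 29 per group that the observed sputum rate implies). The 90% therefore holds at neither 50 nor 30 for a pairwise comparison. The chance of missing a true 0.73 SD difference between the asthma types in one sputum marker is 20.6%, against an implied 10%.

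This rests on equal SDs, approximate normality, unadjusted two-sided alpha 0.05, and 30 evaluable per group. The impact is confined to pairwise sputum comparisons. The array stage, which starts with 5 subjects per condition, is outside these figures. The statement should be corrected, but the error does not by itself call for a change in design or enrolment.

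**What to change.** Replace the power sentence with one at the analysable number. For example, if the sponsor confirms that 50 means accrued after screening:

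> We will accrue 50 subjects per group after screening, expecting about 30 per group with adequate sputum. With 30 evaluable per group (SD 1.0, two-sided alpha 0.05, two-sample t-test), pairwise sputum comparisons have 79% power for 0.73 SD, 80% for 0.74 SD and 90% for 0.85 SD. Pooled asthma (60) vs controls (30) has 90% power for 0.73 SD.

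Then:

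- State which endpoints use the accrued number and which the analysable number. If exhaled nitric oxide, breath condensate and blood markers use all accrued subjects, add that 50 per group gives 95% power for 0.73 SD and 90% for 0.655 SD.
- Update section III.2 (Data Analysis and Data Monitoring) at the same time. It still presents the 10 vs 10 pilot calculation as forthcoming, although the Statistical Analysis section describes that stage as done.
- As a minor clarification, say whether the 300 consented includes a margin over the 222 to 256 that 90 evaluable subjects would need.

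The cost is wording only, with no change in enrolment. The stated power for pairwise sputum comparisons falls from 90% to 79%.
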